#### 5.12.9 Safety assessments

Safety assessments will consist of monitoring and recording all adverse events and serious adverse events, the regular monitoring of hematology, blood chemistry and urine values, regular measurement of vital signs and the performance of physical examinations.

These assessments should be performed within  $\pm 2$  days of the scheduled day of assessment except for adverse events that will be evaluated continuously through the study. Safety and tolerability will be assessed according to the NIH/NCI CTC

[http://evs.nci.nih.gov/ftp1/CTCAE/CTCAE\\_4.03\\_2010-06-14\\_QuickReference\\_8.5x11.pdf](http://evs.nci.nih.gov/ftp1/CTCAE/CTCAE_4.03_2010-06-14_QuickReference_8.5x11.pdf)

#### 5.12.10 Treatment compliance

Records of study medication used, dosages administered, and intervals between visits will be recorded during the study. Drug accountability will be noted and patients will be asked to return all unused study medication.

#### 5.12.11 Adverse events

Tolerability will be assessed using the NCI Common Toxicity Criteria for Adverse Events, version 4.0

[http://evs.nci.nih.gov/ftp1/CTCAE/CTCAE\\_4.03\\_2010-06-14\\_QuickReference\\_8.5x11.pdf](http://evs.nci.nih.gov/ftp1/CTCAE/CTCAE_4.03_2010-06-14_QuickReference_8.5x11.pdf)

Information about all adverse events, whether volunteered by the subject, discovered by investigator questioning, or detected through physical examination, laboratory test or other means, will be collected and recorded and followed as appropriate.

An adverse event is the appearance or worsening of any undesirable sign, symptom, or medical condition occurring after starting the study drug even if the event is not considered to be related to study drug. Medical conditions/diseases present before starting study drug are only considered adverse events if they worsen after starting study drug. Abnormal laboratory values or test results constitute adverse events only if they induce clinical signs or symptoms, are considered clinically significant, or require therapy.

The occurrence of adverse events should be sought by non-directive questioning of the patient at each visit during the study. Adverse events also may be detected when they are volunteered by the patient during or between visits or through physical examination, laboratory test, or other assessments. As far as possible, each adverse event should be evaluated to determine:

1. the severity grade (mild, moderate, severe) or (grade 1-4)
2. its relationship to the study drug(s) (suspected/not suspected)
3. its duration (start and end dates or if continuing at final exam)
4. action taken (no action taken; study drug dosage adjusted/temporarily interrupted; study drug permanently discontinued due to this adverse event; concomitant medication taken; non-drug therapy given; hospitalization/prolonged hospitalization)
5. whether it constitutes a serious adverse event (SAE)

All adverse events should be treated appropriately. Such treatment may include changes in study drug treatment including possible interruption or discontinuation, starting or stopping concomitant treatments, changes in the frequency or nature of assessments, hospitalization, or any other medically required intervention. Once an adverse event is detected, it should be followed until its resolution, and assessment should be made at each visit (or more frequently, if necessary) of any changes in severity, the suspected relationship to the study drug, the interventions required to treat it, and the outcome.

Information about common side effects already known about the investigational drug can be found in the [Investigators' Brochure]. This information should be included in the patient informed consent and should be discussed with the patient during the study as needed.

#### 5.12.12 Serious adverse events

An adverse event is considered serious if it results in **ANY** of the following outcomes:

- 1) Death
- 2) A life-threatening adverse event
- 3) An adverse event results in inpatient hospitalization or prolongation of existing hospitalization for  $\geq 24$  hours
- 4) A persistent or significant incapacity or substantial disruption of the ability to conduct normal life functions
- 5) A congenital anomaly/birth defect.
- 6) Important Medical Events (IME) that may not result in death, be life threatening, or require hospitalization may be considered serious when, based upon medical judgment, they may jeopardize the patient or subject and may require medical or surgical intervention to prevent one

#### 5.12.13 Novartis instructions for rapid notification of serious adverse events

The principal investigator has the obligation to report all serious adverse events to the FDA, IRB and Novartis Pharmaceuticals Drug Safety and Epidemiology Department (DS&E).

All events reported to the FDA by the investigator are to be filed utilizing the Form FDA 3500A (MedWatch Form).

**All events must be reported, by [contact]), to Novartis Pharmaceuticals DS&E Department within 24 hours of learning of its occurrence.** This includes serious, related, labeled (expected) and serious, related, unlabeled (unexpected) adverse experiences. All deaths during treatment or within 30 days following completion of active protocol therapy must be reported within 5 working days.

Any serious adverse event occurring after the patient has started the treatment to until 4 weeks after the patient has stopped study participation must be reported. This includes the period in which the study protocol interferes with the standard medical treatment given to a patient (e.g. treatment withdrawal during washout period, change in treatment to a fixed dose of concomitant medication).

Serious adverse events occurring more than 4 weeks after study discontinuation need only be reported if a relationship to the Novartis study drug (or therapy) is suspected.

For Comparator Drugs/Secondary Suspects (Concomitant Medications), all serious adverse experiences will be forwarded to the product manufacturer by the investigator.

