### **5. TREATMENT PLAN**

#### **5.1 Treatment Regimen**

The investigational therapy used in the course of this study is BKM120. Treatment with BKM120 starts 2 weeks prior to cisplatin and radiotherapy and continues until the end of radiotherapy.

Study medication will be self-administered by the patients continuously throughout radiation. In order to assure compliance with protocol procedures drug administration will be thoroughly explained to the patients. During the study, BKM120 will be administered orally. It is given every day including weekend days. Administration of BKM120 stops with the end of radiotherapy. If radiation is held due to toxicity, BKM120 and cisplatin will be held as well. If cisplatin is held due to toxicity, BKM120 and radiation will continue. If BKM120 is held due to toxicity, cisplatin and radiation will continue. Medication labels will comply with US legal requirements and be printed in English. The storage conditions for study drug will be described on the medication label.

BKM120 will be provided by Novartis Pharmaceuticals free of charge. BKM120 is formulated as capsules for oral administration of 10mg and 50mg strength. Capsules are packaged in bottles. BKM120 capsule cannot be crushed and has to be swallowed. It cannot be given via enteral feeding tube.

If vomiting occurs, no attempt should be made to replace the vomited dose.

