## 5.6 Follow-up for dose-limiting toxicities

Patients whose treatment is interrupted or permanently discontinued due to an adverse event or clinically significant laboratory value, must be followed as outlined in Table 10, at least once a week for 4 weeks, and subsequently at 4-week intervals, until resolution or stabilization of the event, whichever comes first. If a patient requires a dose delay of > 14 days from the intended day of the next scheduled dose, then the patient should be discontinued from the treatment but will only come off study if dead or due to refusal to continue on the study. All patients must be followed for adverse events and serious adverse events for 28 days following the last dose of BKM120.

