## **5.7 Monitoring of BKM120 suspected toxicities**

Patients whose treatment is interrupted or permanently discontinued due to an adverse event or clinically significant laboratory value, must be followed as outlined in Table 10, at least once a week for 4 weeks, and subsequently at 4-week intervals, until resolution or stabilization of the event, whichever comes first. If a patient requires a dose delay of > 14 days from the intended day of the next scheduled dose, then the patient should be discontinued from study treatment. If the patient requires more than 2 dose reductions, the patient should be discontinued from study treatment. All patients must be followed for adverse events and serious adverse events for 28 days following the last dose of BKM120. All SAEs must be reported to Novartis as detailed in section 5.12.11 and 5.12.12.

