## **5.8 Agent Administration**

### **5.8.1 BKM120 Administration**

The study drug BKM120 will be self-administered (by the patients themselves). The investigator will instruct the patient to take the study drug exactly as specified in the protocol. BKM120 will be administered on a continuous once daily dosing schedule. Patients should be instructed to take the dose of BKM120 daily in the morning, one hour after a light breakfast (morning meal) at approximately the same time each day. BKM120 should be taken with a glass of water and consumed over as short a time as possible. Patients should swallow the capsules as a whole and not chew them. Do not crush capsule. Patients should continue to fast for 2 hours after the administration of each BKM120 dose.

If vomiting occurs during the course of treatment, no re-dosing of the patient is allowed before the next scheduled dose. The occurrence and frequency of any vomiting during a treatment must be noted as an adverse event. In addition, on the days of full pharmacokinetic sampling, the exact time of any episodes of vomiting within the first 4 hours post-dosing on that day and within the first 4 hours following the previous day's dosing must be noted whenever possible.

If the patient forgets to take her/his dose AFTER 6:00 PM, then the dose should be withheld that day and BKM120 should be restarted the following day.

Patients must avoid consumption of St. John's Wort, Seville oranges, grapefruit or grapefruit juice, grapefruit hybrids, pummelos and exotic citrus fruits from 7 days prior to the first dose of study medication and during the entire study treatment period due to potential CYP3A4 interaction with the study medication. Patients must avoid concomitant intake of strong and moderate CYP3A4/5 inhibitors and inducers. Orange juice is allowed.

All dosages prescribed and dispensed to the patient and all dose changes during the study must be recorded. If a patient requires a BKM120 dose delay of >14days from the previous dose, the patient must be discontinued from treatment but will only come off study if dead or due to refusal to continue on the study. Patients will only require a 28 day follow up visit after the last dose of BKM120.

Medication labels will comply with US legal requirements and be printed in English. They will supply no information about the patient. The storage conditions for study drug will be described on the medication label.

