### **5.13 Duration of Follow Up**

Follow up (FU) for adverse events will take place every 2 weeks after conclusion of BKM120+CRT (EOT) during the first month, then monthly for 3 months, then every 3 months, until first progression, death, or 2 years from study whichever occurs first. See Study Calendar for full details.

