 Serum chemistry - K+, Na+, Ca++, Mg++, LDH, ALT, AST, total bilirubin (direct and indirect), creatinine, amylase, GGT, lipase, alkaline phosphatase (fractionated if alkaline phosphatase is grade 2 or higher), bicarbonate, phosphorus, uric acid, total cholesterol, HDL, LDL, triglycerides, glucose, urea or BUN, albumin, and total protein are required at baseline and at end of treatment. Subsequent assessments always include K+, Na+, Mg++, Ca++, ALT, AST, total bilirubin (direct and indirect), creatinine, alkaline phosphatase, bicarbonate, phosphorus, glucose, urea or BUN, albumin, and total protein BUT, lipase, total cholesterol, HDL, LDL, triglycerides should be obtained on Day 1 of CRT and EOT  Coagulation - PT or INR, PTT: Day 1 of CRT and EOT

 Patients must be fasting overnight for at least 8 hours. Additional measurements may be performed as clinically indicated.

 Patients will be assessed weekly for adverse events for the duration of the treatment (2 weeks of BKM120 and 7 weeks of BKM120+CRT = 9 weeks) and every 2 weeks after conclusion of BKM120+CRT (EOT) during the first month, then monthly for 3 months, then every 3 months, until first progression, death, or 2 years post study entry whichever occurs first.

 Follow up (FU) will take place every 2 weeks after conclusion of BKM120+CRT (EOT) during the first month, then monthly for 3 months, then every 3 months, until first progression, death, or 2 years post study entry whichever occurs first. Follow up visits must occur within +/- 14 days of the protocol specified date.

 After first progression, patients will be followed for survival every 3 months until 2 years post study entry.

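### Adverse event follow-up has three unreconciled end points, and the one counted from the last BKM120 dose can close while chemoradiation is still being given

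*Combined protocol and SAP*

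**What the plan says.** Three end points are written.

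1. **Counted from BKM120.** Section 5.7, like Section 5.6, states: "All patients must be followed for adverse events and serious adverse events for 28 days following the last dose of BKM120". Section 5.8.1, directly after the rule for patients taken off BKM120 for a delay of more than 14 days, adds: "Patients will only require a 28 day follow up visit after the last dose of BKM120".
2. **Visit schedule.** Section 5.13 and Table 17 footnotes 9 and 10 set adverse event follow-up "until first progression, death, or 2 years from study whichever occurs first". Footnote 9 also requires weekly assessment through the 9 weeks of treatment. These places speak of adverse events and do not name serious ones separately.
3. **Reporting to the supplier.** Section 5.12.13 requires that any serious event from the start of treatment "until 4 weeks after the patient has stopped study participation must be reported". Later ones "need only be reported if a relationship to the Novartis study drug (or therapy) is suspected", with no end date.

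Three other statements bear on how these interact.

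- Section 5.1: "If BKM120 is held due to toxicity, cisplatin and radiation will continue".
- Section 5.6, on patients discontinued after the long delay: such a patient "will only come off study if dead or due to refusal to continue on the study".
- Table 17 footnote 11: "After first progression, patients will be followed for survival every 3 months until 2 years post study entry". In the post-progression column the adverse event row is blank, but the physical examination row is marked.

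**The concern.** The first rule is tied to one of three concurrent treatments. A patient who stops BKM120 permanently and early goes on with cisplatin and radiation, yet the 28-day clock has already started. These are the patients who tolerated the combination least. If a site follows Sections 5.6, 5.7 and 5.8.1 literally, they are the ones least observed during chemoradiation.

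This matters for a drug that Section 2.1 presents as a radiosensitizer, because toxicity late in the radiation course is part of what the trial should describe. Section 13 rests the estimate of the adverse event rate on the 10 expansion patients and states no time window for it. Sites that apply different rules would contribute different periods of observation to the same proportion.

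Capture after progression is also unclear. Table 17 schedules no adverse event assessment there, while Section 5.12.11 asks for adverse events to be sought at every study visit.

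**Working it through.** **Inputs**

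- BKM120 starts on study day 1, and chemoradiation (CRT) starts 2 weeks later, on study day 15 (Sections 1.1, 5.1, 5.11).
- Radiation: 35 fractions, 5 per week for 7 weeks (Section 5.9).
- Cisplatin: CRT days 1, 8, 15, 22, 29, 36 and 43 (Section 5.8.2).
- Follow-up: 28 days after the last BKM120 dose (Sections 5.6, 5.7).
- Assumptions: CRT starts on a Monday, there are no treatment breaks, and BKM120 is stopped for good, not held and resumed.

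**The plan's own figure.** 2 + 7 = 9 weeks = 63 days, as Table 17 footnote 9 states.

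**Last treatments.** Last fraction: 14 + 6 × 7 + 5 = study day 61 (CRT day 47). Last cisplatin: 14 + 43 = study day 57.

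**When the window closes.** With the last BKM120 dose on study day d, it closes on day d + 28.

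- Before the last fraction if d + 28 < 61, that is d ≤ 32.
- Before the nominal end of CRT (day 63) if d + 28 < 63, that is d ≤ 34.

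| Last BKM120 dose (study day) | Window closes (study day) | CRT day | Relative to last fraction |
|---|---|---|---|
| 10 | 38 | 24 | 23 days before |
| 14 | 42 | 28 | 19 days before |
| 21 | 49 | 35 | 12 days before |
| 28 | 56 | 42 | 5 days before |
| 32 | 60 | 46 | 1 day before |
| 63 (full course) | 91 | 77 | 30 days after |

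**What is still to come in the day 10 case.** By CRT day 24, 3 full weeks and 3 further weekdays have been treated: 3 × 5 + 3 = 18 fractions. That leaves 35 − 18 = 17 fractions, and the cisplatin doses on CRT days 29, 36 and 43.

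**Spread between the rules.** For a full course, the BKM120 rule closes on day 63 + 28 = 91. For a patient who stays in the study to 2 years, the supplier rule closes on about day 730 + 28 = 758.

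**Weight of one patient.** In the 10-patient expansion cohort, counting or missing one patient's event moves the rate by 1/10 = 10 percentage points.

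**When study participation stops.** Sections 5.6 and 5.8.1 allow only death or refusal, for patients discontinued after the long delay. Section 5.14 lists nine reasons for ending treatment or participation, including progression and loss to follow-up. Appendix B takes a patient off study who needs other anticancer therapy. Table 11 takes patients off the study for some grade 4 events and off BKM120 for others. The 4-week clock in Section 5.12.13 could therefore start during CRT or near 2 years.

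**The case against.** The strongest reply is that the rules serve different purposes and do not compete. Sections 5.6 and 5.7 concern dose-limiting toxicity and suspected BKM120 toxicity, so their 28 days can be read as a minimum. Section 5.7 itself sends serious event reporting to the safety parts of Section 5.12. Weekly visits cover all of CRT under Table 17, and Section 5.12.13 requires every serious event from the start of treatment. If BKM120 is held and resumed, the last dose moves later and the gap may vanish.

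Most of this stands, and it makes the gap conditional. It does not remove it: the restrictive wording in Section 5.8.1 turns the 28 days into a limit for exactly the patients at issue, and no section says which rule prevails.

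A reader might go further in four ways that the documents do not support.

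- **That nothing looks for events after progression.** A physical examination is marked there, Section 5.12.3 requires findings that qualify as adverse events to be recorded, and Section 5.12.11 requires questioning at each visit. Capture is inconsistent, not absent.
- **That every patient stays reportable for 2 years plus 4 weeks, so that recurrence and salvage treatment contaminate the safety data.** The death-or-refusal wording covers only those with the long delay. Under Appendix B, new anticancer therapy ends participation.
- **That about half of patients would contribute post-progression serious events.** The cure rate of around 50% in Section 2.1 is a historical figure and gives no rate of such events.
- **That a planned serious event rate by dose level is distorted.** Section 13 plans none.

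**Conclusion.** The inconsistency is real and should be corrected. If the BKM120-based rule governs, a patient whose last dose falls by about study day 32 leaves adverse event follow-up before radiation ends. In the day 10 case that is nearly half the fractions (17 of 35) and 3 of 7 cisplatin doses. If Table 17 governs, there is no gap during CRT. For a patient who completes BKM120 there is none under either reading. The day counts assume a Monday start and no breaks. The documents do not say how many patients would stop this early.

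The gap between day 91 and day 758 should not be read as the size of the problem, since it compares rules with different purposes. For a progression-free patient followed to 2 years, the second and third rules differ by only 28 days (730 against 758).

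The MTD decision is not affected. Section 5.5 sets its own dose-limiting toxicity window of under 28 days from the last BKM120 dose, which lies inside the shortest follow-up rule. Sample size and escalation probabilities do not change. What is exposed is the completeness of safety observation in early stoppers, and the meaning of the Section 13 adverse event rate, which has no window.

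**What to change.** Reconcile Sections 5.6, 5.7, 5.8.1, 5.12.13 and Table 17 as follows.

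- Make the 28 days a minimum, counted from the last of BKM120, cisplatin and radiation.
- Remove the restriction to a single visit in Section 5.8.1, so that patients who stop BKM120 early stay on the Table 17 schedule.
- Define when study participation stops, consistently with Sections 5.6, 5.8.1 and 5.14, Table 11 and Appendix B.
- State in Table 17 whether adverse events are to be sought at post-progression visits, in line with Section 5.12.11.
- In Section 13, report the adverse event rate for the period on treatment plus 28 days, and show later events separately.

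Keep the longer adverse event follow-up and the broader supplier reporting. Cutting either to make the windows equal would lose data that the plan now collects.

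The cost is a wording amendment and one extra line in the safety tables. The visits needed for early stoppers are already in Table 17.

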#### 5.12.14 Pregnancies

To ensure patient safety, each pregnancy in a patient on study treatment must be reported to Novartis within 24 hours of learning of its occurrence. The pregnancy should be followed up for 3 months after the termination of the pregnancy to determine outcome, including spontaneous or voluntary termination, details of the birth, and the presence or absence of any birth defects, congenital abnormalities, or maternal and/or newborn complications.

Pregnancy should be recorded on a Clinical Study Pregnancy Form and reported by the investigator to the oncology Novartis Drug Safety and Epidemiology (DS&E) department. Pregnancy follow-up should be recorded on the same form and should include an assessment of the possible relationship to the Novartis study treatment of any pregnancy outcome. Any SAE experienced during pregnancy must be reported on the SAE Report Form.

Pregnancy outcomes must be collected for the female partners of any males who took study treatment in this study. Consent to report information regarding these pregnancy outcomes should be obtained from the mother.

### **5.13 Duration of Follow Up**

Follow up (FU) for adverse events will take place every 2 weeks after conclusion of BKM120+CRT (EOT) during the first month, then monthly for 3 months, then every 3 months, until first progression, death, or 2 years from study whichever occurs first. See Study Calendar for full details.

